### 13.2 Sample Size, Accrual Rate and Study Duration

We anticipate approximately 12 CLL/SLL patients will be enrolled in the phase I study, using the traditional 3+3 design as described above.

For the phase II study, a Simon two-stage design will be employed whereby a 10% complete response (CR) rate is considered not promising, a 30% complete response rate is considered promising, and the probabilities of a type I error (falsely accepting a non-promising therapy) and type II error (falsely rejecting a promising therapy) are set at 0.10 and 0.10, respectively. In the first stage of this design, 12 CLL/SLL patients will be accrued. All patients will be followed for up to one year. If at least 2 patients achieve CR then an additional 23 CLL/SLL patients will be accrued to the second stage. If 0 or 1 patients achieve CR the study will be terminated and declared negative. The probability of early stopping based on an optimal Simon’s two stage design is 65%. At the end of the trial, if 6 or more patients respond out of a total of 35 patients, then this combination will be considered worthy of further investigation. This design yields at least a 0.90 probability of a positive result if the true response rate is at least 30% and yields a 0.90 probability of a negative result if the true response rate is 10%.

Of note, all patients in the phase I study will be evaluated for response and can be counted in efficacy evaluations in stage 1 of the phase II portion of the trial. An exploratory analysis will also be performed to estimate the rate of CR with confidence intervals in the 29 patients treated at the venetoclax MTD.

For the Richter’s Syndrome Cohort, we plan to accrue 20 additional patients. Given the poor prognosis and lack of a standard of care for this population, we will not have an early stopping rule for this cohort based on efficacy or toxicity.

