**Phase II:**

- Determine the rate of complete response (CR) of duvelisib in combination with the MTD of venetoclax, as defined by the IWCLL 2008 criteria for CLL/SLL or Lugano 2014 Criteria for RS

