**Sample Size:**

We anticipate that approximately 12 CLL/SLL patients will be enrolled in the phase I study, using the traditional 3+3 design as described above.

CONFIDENTIAL

This document is confidential. Do not disclose or use except as authorized.

For the phase II study, a Simon's two-stage design will be employed with 12 CLL/SLL patients accrued to the first stage. All patients will be followed for up to one year. If at least 2 patients achieve a CR then an additional 23 patients will be accrued to the second stage. Patients who receive the MTD of venetoclax in the phase I portion of the trial can also be counted in the analysis of the phase II portion of the trial.

A separate cohort of 20 patients with Richter's Syndrome will be enrolled in parallel with the CLL/SLL cohort in a one stage design.

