### 1.2 Primary Objectives

#### *Phase I*

- Determine the dose limiting toxicities (DLT), maximum tolerated dose (MTD) as well as the recommended phase II dose and safety profile for this combination regimen of duvelisib plus venetoclax for patients with relapsed or refractory CLL/SLL

CONFIDENTIAL

This document is confidential. Do not disclose or use except as authorized.

*Phase II:*

- Determine the best rate of complete response (CR) or complete response with incomplete count recovery (CRi) of duvelisib in combination with the MTD of venetoclax as defined by the IWCLL 2008 criteria for CLL/SLL or Lugano 2014 criteria for RS.

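### The Synopsis and section 13.2 name different phase I patients for the phase II CR analysis, and the stated 0.90 power holds only if those counted respond at least as often as patients at the MTD

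*Combined protocol and SAP*

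**What the plan says.** Two passages say which phase I patients may enter the phase II efficacy analysis.

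- Synopsis, Sample Size: "Patients who receive the MTD of venetoclax in the phase I portion of the trial can also be counted in the analysis"; the analysis meant is that for phase II.
- Section 13.2: "all patients in the phase I study will be evaluated for response and can be counted in efficacy evaluations in stage 1" of phase II. No dose level is named.

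The Synopsis gives the phase II primary objective as "Determine the rate of complete response (CR) of duvelisib in combination with the MTD of venetoclax". Section 1.2 likewise refers to "duvelisib in combination with the MTD of venetoclax as defined by the IWCLL 2008 criteria", and section 1.1 agrees.

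On the design, section 13.2 says "In the first stage of this design, 12 CLL/SLL patients will be accrued". At least 2 CRs open 23 further places, and 6 or more CRs among 35 is a positive result. It then states two operating characteristics without conditions: "This design yields at least a 0.90 probability of a positive result if the true response rate is at least 30" per cent, and that the design "yields a 0.90 probability of a negative result if the true response rate is 10" per cent. It also plans an exploratory analysis to "estimate the rate of CR with confidence intervals in the 29 patients treated at the venetoclax MTD".

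**The concern.** Phase I assigns patients to 100, 200 or 400 mg of venetoclax, so patients at the MTD and all phase I patients are different sets unless everyone is treated at the MTD. Under 13.2, patients assigned below the MTD can enter a test of the CR rate at the MTD.

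Neither passage says how many phase I patients are counted, in what order, or whether counting is obligatory. The phrase about receiving the MTD is also open. Lower-dose patients may later escalate to it (Synopsis, Study Design, Phase I; section 5), so it could mean assigned to the MTD or ever treated at it.

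The stage 1 rule either ends the CLL/SLL study or opens 23 more places, and the 6-of-35 rule is the final verdict. If lower-dose patients reach CR less often than MTD patients, an active combination is more likely to be stopped after stage 1 or declared negative than the plan states.

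**Working it through.** **Inputs from section 13.2.** CR rates 10% (not promising) and 30% (promising); error limits 0.10 and 0.10; stage 1 n = 12, continue if at least 2 CRs; stage 2 n = 23; positive if at least 6 CRs in 35.

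**Step 1. Reproduce the stated design.** With one CR rate p for all patients:

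P(stop) = P(Bin(12, p) ≤ 1)

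P(positive) = Σ over x = 2 to 12 of P(Bin(12, p) = x) × P(Bin(23, p) ≥ 6 − x)

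- p = 0.10: stop = 0.2824 + 0.3766 = 0.659 (plan: 65%); type I error 0.098 (plan: 0.10).
- p = 0.30: stop = 0.0138 + 0.0712 = 0.085; power 0.901 (plan: at least 0.90).

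The plan's figures are right for 35 patients with a common CR rate.

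**Step 2. How many lower-dose patients?** 35 − 29 = 6. This fits about 12 phase I patients split 3 + 3 below the MTD and 6 at it: 6 + 23 = 29. The split is likely but not certain. Rule (4) in section 13.1 adds up to three patients at the candidate MTD. Section 5 adds three more at the MTD who start at 20 mg, and does not say whether they are among the 12. Three lower-dose patients are therefore also shown.

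**Step 3. Power with lower-dose patients inside stage 1.** Let m of the 12 have CR rate q and everyone else p. The stage 1 count is Bin(m, q) + Bin(12 − m, p), the stage 2 count is Bin(23, p), and the cut-offs are unchanged. The documents give no lower-dose CR rate, so q is an assumed range.

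Stopping probability for m = 6, p = 0.30, q = 0.10:

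- No CR: 0.5314 × 0.1176 = 0.0625
- One CR: 0.5314 × 0.3025 + 0.3543 × 0.1176 = 0.2025
- Sum: 0.265

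All results at an MTD rate of 30%:

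| Assumed lower-dose rate q | Power, m = 6 | Wrong stop after stage 1, m = 6 | Power, m = 3 |
|---|---|---|---|
| 30% (same as MTD) | 0.901 | 0.085 | 0.901 |
| 25% | 0.868 | 0.117 | 0.886 |
| 20% | 0.826 | 0.156 | 0.869 |
| 15% | 0.776 | 0.206 | 0.850 |
| 10% | 0.715 | 0.265 | 0.830 |

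The design has almost no reserve: at q = 29% with m = 6, power is already 0.895.

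**Step 4. Type I error under the same replacement.** With m = 6 and an MTD rate of 10%, type I error is 0.026, 0.058 and 0.098 for q = 0%, 5% and 10%. It rises above 0.10 only if lower-dose patients respond more often than MTD patients (0.144 at q = 15%, 0.195 at q = 20%).

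**The case against.** The best defence is that 13.2 largely shows its intent. Phase I patients fill stage 1, the total stays at 35, and an MTD-only estimate in 29 patients is planned alongside. Both passages are permissive, the Synopsis does not restrict counting to MTD patients in so many words, and its set lies inside the 13.2 set. On this view the Synopsis is simply not aligned with the statistical section.

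The size of the power loss also rests on assumed rates, and 0.72 needs a threefold gap (10% against 30%). Several passages point to a smaller gap. Lower-dose patients may escalate to the MTD. Duvelisib inhibits CYP3A4 (sections 5.4.6 and 7.4.1.3), which is the main route of venetoclax metabolism (section 8.2.1). Section 2.3 reports venetoclax activity at every dose studied from 150 mg, which covers 200 mg but not 100 mg.

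Much of this stands. The design arithmetic is sound, and the loss may be at the small end. It does not remove the point. The 29-patient estimate is exploratory and does not govern either decision rule, and 13.2 still states 0.90 power without the condition that a mixed stage 1 needs.

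Three stronger readings are tempting, but the documents do not support them.

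- **Two incompatible mandatory rules.** Both passages say what can be done, not what must be.
- **Inflated type I error because phase I patients are added to the 12.** Section 13.2 fixes the final rule at 6 CRs among a total of 35, which leaves no room for extra patients.
- **Choosing the counted set after seeing responses.** No passage plans such a choice; the rule is merely silent on it.

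**Conclusion.** The point holds for the definition of the counted set and for power. The Synopsis and 13.2 name different phase I patients for the primary phase II analysis, and 13.2 admits patients assigned below the dose that the objective concerns.

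Power of at least 0.90 needs counted lower-dose patients to reach CR at least as often as MTD patients. If six fill stage 1 places and the MTD rate is 30%, power is 0.87 to 0.72 for lower-dose rates of 25% to 10%, and the chance of wrongly stopping after stage 1 rises from 0.085 to between 0.117 and 0.265. With three such patients, power is 0.89 to 0.83.

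These figures assume that counted patients replace stage 1 places within the 35 and that the cut-offs are unchanged. The number of lower-dose patients is inferred from the 29, and their CR rate is assumed. Type I error is not at risk while the lower-dose rate is no higher than the MTD rate, so a general claim that both stated error rates fail would be wrong.

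**What to change.** Put one rule in both the Synopsis and section 13.2. It should say, by assigned dose level, which phase I CLL/SLL patients count. It should also say that they fill places within the 12 in enrolment order, that the total stays at 35, and that this applies regardless of response. Then choose one of two versions.

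- **(a) MTD only.** Count only patients assigned to the MTD in the primary test. Summarise lower-dose patients separately, including any who later escalate, and drop the 29-patient analysis. This matches the objective and keeps the stated power and type I error. It costs up to six more enrolments at the MTD within the 35, with their one-year assessments, before the stage 1 decision.
- **(b) Mixed stage 1.** Keep lower-dose patients and the 29-patient MTD analysis. State that power of at least 0.90 needs a lower-dose CR rate at or above the MTD rate, and that type I error of at most 0.10 needs a lower-dose rate no higher than the MTD rate. Give both figures over a stated range of lower-dose rates. This needs no further patients, but power and type I error become conditional.

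Both versions are otherwise changes of wording.

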**Accelerated ramp up for RS patients:**

CONFIDENTIAL

This document is confidential. Do not disclose or use except as authorized.

Given the potential for rapidly progressive RS, these RS patients will also have the option to undergo an accelerated venetoclax ramp-up in the inpatient setting modeled after another study of venetoclax plus chemotherapy that was recently reported ([name] et al., ICML, 2019). In that study, venetoclax was safely ramped up in a daily fashion for 20 RS patients, who were monitored closely in the inpatient setting, with no evidence of tumor lysis syndrome. The venetoclax is dosed at 20 mg for day 1, and if no TLS is observed on labs done 6-8 hours and 24 hours later, then the dose is ramped up to 50 mg on day 2, 100 mg on day 3, 200 mg on day 4, and 400 mg on day 5 if the daily labs done 6-8 hours and 24 hours later continue to show no TLS. If laboratory TLS does occur, the next day's dose will be held until there is improvement in the TLS, at which point escalation to the next dose may occur

Study visits will occur weekly through cycles 1-2, once per cycle during cycles 3-7, every two cycles from cycle 7-13, and every 3 cycles thereafter through cycle 60. After cycle 60, patients will return for study visits every six cycles until they are removed from treatment. Patients will be treated with duvelisib plus venetoclax for up to one year followed by venetoclax monotherapy until disease progression without clinical benefit, death, unacceptable toxicity, withdrawal of consent, physician/patient discussion of discontinuation based on objective disease response, or they elect to go on a new CLL or Richter's directed therapy.

CT of the neck, abdomen, pelvis and neck (CLL) or full body PET/CT (Richter's) scans will be mandatory at C4D1, C7D1, C13D1, and then at the discretion of the treating investigator or approximately every six cycles thereafter. Bone marrow biopsy will be mandatory at study entry and at the C7D1, C13D1, and C25D1 re-staging visits. Subsequent bone marrow biopsies will be performed as clinically indicated thereafter at the discretion of the treating investigator.

Patients will be evaluated for MRD negativity in the peripheral blood approximately every three months and with each bone marrow biopsy (except the baseline biopsy). MRD testing will be performed by 4-color flow cytometry with a sensitivity of  $10^{-4}$  and when possible also by ClonoSEQ (Adaptive), a next generation sequencing technology.

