#### 7.4.1.3 *Concomitant use with other agents:*

CYP3A4 has been identified as the primary contributor to the metabolism of duvelisib. In Study IPI-145-01, exposure to duvelisib increased approximately 4-fold in the presence of the strong CYP3A inhibitor ketoconazole, and decreased approximately 80% in the presence of rifampin, a CYP3A inducer. For these reasons, the concomitant use of drugs or foods that are strong inhibitors or inducers of CYP3A is not allowed during treatment with duvelisib.

In vitro studies in human liver microsomes demonstrated that duvelisib and its primary metabolite IPI-656 are reversible inhibitors of CYP3A4 and CYP2C8 and mechanism-based inhibitors of CYP3A4.

Coadministration of duvelisib (25 mg BID for 5 days) with MDZ (a sensitive CYP3A substrate) resulted in an approximate 4-fold increase in MDZ systemic exposure (AUC) compared to administration of MDZ alone. Systemic exposure to other medications that are substrates for CYP3A4 may be increased in subjects receiving duvelisib. Caution should be used if duvelisib is administered concomitantly with drugs that are substrates for CYP3A, particularly those with a narrow therapeutic range. Drugs that are substrates for CYP3A should be used only if medically necessary and therapeutic alternatives are not available.

Based on plasma concentrations following administration of 25 mg BID, duvelisib is not expected to increase the exposure of medications metabolized via CYP2C8; however, a clinical study with a CYP2C8 substrate has not been conducted. Medications that are metabolized via CYP2C8 may be used as medically indicated but with caution.

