***Evaluation of Toxicity in Phase II***

We will closely monitor treatment-related toxicity for all participants. Participants in the phase II portion of the study who meet DLT criteria during the first cycle of combination treatment as specified in section 5.3 will be analyzed by the following method:

Sequential Pocock-type stopping boundaries will be used to monitor the unexpected toxicity rate (Ivanova et al., 2005). Accrual will be halted and the Data Safety Monitoring Committee consulted if excessive numbers of unexpected toxicities are seen, that is, if the number of toxicities is equal to or exceeds  $b_n$  out of  $n$  patients who received at least one dose of combination therapy (see table 11). For example, if 6 or more out of the first 20 patients ( $\geq 40\%$ ) experience unacceptable toxicities the study will be stopped; or if 8 or more out of the first 30 patients ( $\geq 26\%$ ) experience unacceptable toxicities the study will be stopped. With these rules, the probability of early stopping the trial if the true rate of toxicity is  $\leq 10\%$  does not exceed 0.05, if the true toxicity rate is 30% the probability of early stopping is 0.865 (table 12).

Table 11: The trial will be stopped if the number of toxicities is equal to or exceeds  $b_n$  out of  $n$  patients evaluable for toxicity.

Number of Patients, $n$	Boundary, $b_n$
1	-
2	2
3	3
4	3
5	3
6	3
7	4
8	4
9	4
10	4
11	5
12	5
13	5
14	5
15	5
16	6
17	6
18	6
19	6
20	6
21	6
22	7
23	7
24	7
25	7
26	7
27	7
28	8
29	8
30	8
31	8
32	8
33	8
34	9
35	9

Table 12: Probabilities of early stopping at different true but unobserved toxicity rates.

Toxicity Rate	0.10	0.20	0.30	0.40	0.50	0.60
Probability of early stopping	0.048	0.436	0.865	0.988	0.999	1.00

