***Phase II Study (Richter’s Syndrome Cohort):***

In a previous study with a commonly used chemoimmunotherapy regimen for RS, dose-adjusted EPOCH-R, the CR rate was 20%. We base this as the null hypothesis. With the addition of

CONFIDENTIAL

This document is confidential. Do not disclose or use except as authorized.

venetoclax, we hypothesize that the CR rate will be 45% or higher. Twenty patients will be enrolled and if 7 or more patients achieve CR we will regard the treatment efficacious. Conversely, if 6 or fewer patients achieve CR, we will regard the treatment inefficacious. With this design, the probability of concluding the treatment efficacious is 0.87 if the true but unknown response rate is 45% and 0.09 if the true rate is 20%. This decision rule is calculated using the exact binomial method. Table 1 below shows the operating characteristics of this design.

Table 1. Operating Characteristics

	True but Unknown CR Rate					
	20%	25%	30%	35%	40%	45%
Prob( $\geq 7$ CR in 20)	0.09	0.21	0.39	0.58	0.75	0.87

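### No DLT count pauses accrual in the RS cohort: 13.2 exempts it from toxicity stopping while 13.1 monitors all phase II participants, and the two must be reconciled

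*Combined protocol and SAP*

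**What the plan says.** Section 13.2 sets the cohort size, "For the Richter’s Syndrome Cohort, we plan to accrue 20 additional patients", and then, giving as its reason "Given the poor prognosis and lack of a standard of care for this population", says that "we will not have an early stopping rule for this cohort based on efficacy or toxicity".

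In section 13.1, the part on toxicity in phase II opens with "We will closely monitor treatment-related toxicity for all participants". It takes phase II participants who meet the section 5.3 DLT criteria in the first cycle of combination treatment and applies a Pocock-type boundary (Table 11, n = 1 to 35). Reaching the boundary halts accrual and brings in the DSMC. This part follows the CLL/SLL phase II heading, and 35 is the CLL/SLL sample size.

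On phase I, 13.2 says "We anticipate approximately 12 CLL/SLL patients will be enrolled in the phase I study". The DLT/MTD objective in 1.2 names CLL/SLL only, and 1.1 describes a weekly venetoclax ramp-up from 10 mg.

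In phase II, section 5 gives RS patients the option of an inpatient daily ramp-up that reaches 400 mg on day 5. It is modelled on an external study of venetoclax plus chemotherapy: "In that study, venetoclax was safely ramped up in a daily fashion for 20 RS patients", with no TLS seen.

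**The concern.** Two things are at issue. First, the documents do not give one answer on whether RS patients are under a toxicity boundary. Read alone, 13.1 covers them; 13.2 says they are not covered. Nor does the plan say whether an RS DLT counts towards the Table 11 boundary. If both cohorts were pooled, 35 + 20 = 55 patients would run past the table's last row.

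Second, if 13.2 governs, RS is the one phase II cohort with no numeric trigger, although it may use a ramp-up schedule that phase I did not include. The stated reason, poor prognosis without a standard of care, is a good argument for completing the efficacy estimate. It does not explain why accrual should not even pause for DSMC advice if DLTs accumulate. At stake is how many RS patients are enrolled before anyone is obliged to look.

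**Working it through.** **Inputs.** Table 11 boundary b_n (13.1): none at n=1; 2 at n=2; 3 at n=3–6; 4 at 7–10; 5 at 11–15; 6 at 16–21; 7 at 22–27; 8 at 28–33; 9 at 34–35. RS cohort size 20 (13.2). The true DLT rate p is not given for RS, so a range is shown.

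**Method.** Exact recursion, one look per patient. Let f_n(k) be the probability of k DLTs in n patients with no boundary yet reached:

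f_n(k) = f_{n−1}(k)(1−p) + f_{n−1}(k−1)p.

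Mass with k ≥ b_n is removed as a halt at n. P(halt) is the sum of the removed mass; mean treated is Σ n·P(halt at n) + N·P(no halt). The first steps can be done by hand. At n=2 a halt needs two DLTs, p². The next possible halt is at n=4, with probability 2p³(1−p). At p=0.30 these are 0.090 and 2 × 0.027 × 0.70 = 0.0378, so 0.128 by patient 4.

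**Step 1: reproduce the plan's figures (N=35).**

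| True rate | Table 12 | Recomputed |
|---|---|---|
| 10% | 0.048 | 0.049 |
| 20% | 0.436 | 0.438 |
| 30% | 0.865 | 0.866 |
| 40% | 0.988 | 0.988 |
| 50% | 0.999 | 1.000 |
| 60% | 1.00 | 1.000 |

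Agreement is within about 0.002. A Pocock-type boundary built from a 10% rate and a total stopping probability of at most 0.05 returns every b_n in Table 11, so the method is the plan's own.

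**Step 2: RS as written.** The formal halt probability is 0 at every rate; 20 are treated, with 20p expected DLTs: 2, 4, 6, 8 and 10 at 10 to 50%.

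**Step 3: rows 1–20 applied to RS alone.**

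| True DLT rate | P(pause) | Mean treated |
|---|---|---|
| 10% | 0.038 | 19.5 |
| 15% | 0.128 | 18.6 |
| 20% | 0.281 | 17.2 |
| 25% | 0.472 | 15.3 |
| 30% | 0.657 | 13.2 |
| 40% | 0.902 | 9.3 |
| 50% | 0.985 | 6.5 |

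The means include runs that never pause and count 20. Given that a pause occurs, the mean is 9.6, 8.1 and 6.3 patients at 30, 40 and 50%.

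**Step 4: recalibrated to N=20.** The same boundary type, with at most 5% at a 10% DLT rate, differs only at n=11, 12 (4 instead of 5) and n=16, 17 (5 instead of 6). It pauses with probability 0.049, 0.328, 0.700, 0.919 and 0.988 at 10 to 50%.

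Steps 3 and 4 assume each DLT is known before the next patient enrols. Cycle 1 can last up to 49 days (5.1.1), so several patients may enrol while earlier outcomes are pending.

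**The case against.** The exemption is deliberate, disclosed and reasoned, and 2.6 calls the RS cohort exploratory. Poor prognosis can also bear on how much toxicity is acceptable. That stands as a reason to choose the reference DLT rate with care. It does not explain the lack of any pause.

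A reader might infer that RS accrual would run to 20 unsupervised. The documents do not support that. The DSMC reviews up to four times a year (5.3.1), or more often if required, and may receive DLT information (12.2). The accelerated ramp-up is optional and inpatient, needs written approval from the Overall PI (5.1.2.2), and holds the next dose if laboratory TLS occurs. Section 7.5.2 adds expedited reporting of all grade 5 and unexpected grade 4 events. These safeguards are real, but they act at discretion or per patient.

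A reader might also lean on the interaction data. The roughly four-fold exposure rise in 7.4.1.3 is for midazolam; the documents give no such figure for venetoclax. The interaction is not specific to RS either: phase I combined the same two drugs, and 2.5 gives the interaction as the reason for cautious initial dosing. What is new is the speed of the ramp-up. Likewise, 0 TLS in 20 leaves a one-sided 95% upper limit of 1 − 0.05^(1/20) = 13.9%, but this concerns TLS with another regimen and says nothing about the DLT rate. There is also some reassuring evidence: 2.6 reports venetoclax monotherapy toxicity in RS similar to CLL/SLL, and section 5 reports no TLS at the 10 mg start in phase I.

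The strongest point is cost. The boundary is tuned to a 10% rate, and no section sets an acceptable rate for RS. Section 5.3 counts febrile neutropenia of any duration, and events count unless clearly unrelated. Entry is allowed at a neutrophil count of 500, with the threshold waived for significant marrow involvement (3.1.5). A background rate above 10% is therefore possible, and the chance of an unnecessary pause rises with it.

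**Conclusion.** The point holds in this form: 13.1 and 13.2 disagree on whether RS is under the toxicity boundary, and on the explicit wording of 13.2 no cohort-level DLT count pauses RS accrual. The plan's own boundary on 20 patients would pause with probability 0.66 at a 30% DLT rate and 0.90 at 40%, with 13.2 and 9.3 treated on average instead of 20. These are upper bounds on the saving, because they assume immediate knowledge of each DLT.

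The documents do not support two further inferences. The missing rule does not bias the decision at 7 or more CRs in 20; the operating characteristics given there (0.09 at 20%, 0.87 at 45%) recompute as 0.087 and 0.870. Nor can the downside be put at 4% without qualification: that figure holds only if 10% is the acceptable DLT rate.

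This is an inexpensive improvement to safety monitoring plus a contradiction to resolve. It does not invalidate the cohort.

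**What to change.** In 13.2, strike toxicity from the exemption and keep the decision not to stop for efficacy. State that RS patients are monitored separately and do not count towards the CLL/SLL boundary. Use rows 1–20 of Table 11, or the same boundary type recalibrated to N=20 at a stated acceptable DLT rate, as an accrual pause with DSMC review, not termination. In 13.1, say which cohort each boundary covers. At each review, tabulate RS DLTs by ramp-up type (accelerated or weekly). No dose or treatment rule changes.

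The drafting cost is small: the boundary and DLT definition exist. The sponsor must choose and justify an acceptable RS DLT rate. With rows 1–20, the chance of an unnecessary pause is 4% if that rate is 10%, 13% if 15% and 28% if 20%. If the sponsor prefers to keep the exemption, 13.1 should exclude RS explicitly and 13.2 should give a reason that addresses toxicity.
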